10.7.6 Reporting of SADEs

SADE reporting to the Sponsor

NOTE: There are additional reporting obligations for medical device deficiencies that are potentially related to SAEs that must fulfill the legal responsibility to notify appropriate regulatory authorities and other entities about certain safety information relating to medical devices being used in clinical studies.

- Any device deficiency that is associated with an SAE must be reported to the Sponsor within 24 hours after the Investigator determines that the event meets the definition of a device deficiency.
- The Sponsor will review all device deficiencies and determine and document in writing whether they could have led to an SAE. These device deficiencies will be reported to the regulatory authorities and IRBs/IECs as required by national regulations.
- Contacts for SAE reporting can be found in Investigator file.

10.8 APPENDIX 8: COUNTRY-SPECIFIC REQUIREMENTS

10.8.1 Germany-specific requirements

For Section 8.3.1 Time period and frequency for collecting AE and SAE information and Section 10.3.3 Recording and follow-up of AE and/or SAE

This study will comply with the German GCP ordinance (§ 12 (4) GCP-V) regarding the reporting of SAEs as described below.

- The Investigator will submit any SAE data to the Sponsor immediately after obtaining knowledge.
- If the electronic system is unavailable, then the site will use the paper SAE data collection tool to immediately report the event, after obtaining knowledge.

For Section 10.1.3 Informed consent process

“Legally authorized representative” is not applicable for adult participants in Germany.

10.9 APPENDIX 9: CONTINGENCY MEASURES FOR A REGIONAL OR NATIONAL EMERGENCY THAT IS DECLARED BY A GOVERNMENTAL AGENCY

A regional or national emergency declared by a governmental agency (eg, public health emergency, natural disaster, pandemic, terrorist attack) may prevent access to the clinical trial site.

Contingency procedures are suggested for an emergency that prevents access to the study site, to ensure the safety of the patients, to consider continuity of the clinical study conduct, protect trial integrity, and assist in maintaining compliance with Good Clinical Practice in Conduct of Clinical Trials Guidance. Sponsor agreement MUST be obtained prior to the implementation of these procedures for the duration of the emergency.

During the emergency, if the site will be unable to adequately follow protocol mandated procedures, screening and enrollment may be temporarily delayed/halted. Attempts should be made to perform all assessments in accordance with the approved protocol to the extent possible. In case this is not possible due to a temporary disruption caused by an emergency, focus should be given to assessments necessary to ensure the safety of patients and those important to preserving the main scientific value of the study.

For European countries contingency measures are currently only applicable for the COVID-19 pandemic.

Procedures to be considered in the event of a regional or national emergency declared by a governmental agency:

- If onsite visits are not possible, visit windows may be extended for assessment of safety and/or efficacy data that cannot be obtained remotely. Possibility of visit extension must be discussed on a case by case basis with the Sponsor considering first of all subject's safety and best interests.
- If onsite visits or alternative location (out of patient's home) are not possible, visits will have be performed at home by a trained healthcare professional and if allowed by local competent authorities for the following but not limited to:
 - Monitoring of injection site reactions, AEs and SAEs
 - Collect study samples for safety, and pregnancy test (if applicable)
 - Perform study examinations (eg, Measuring vital signs)
- IMP Injection Training: In case of emergency (eg, natural disaster, pandemic) different training ways (eg, training remotely with instruction provided by phone) can be performed (and will be documented in the patient's study file).
- After Sponsor agreement is obtained, the IMP may be supplied from the site to the participant via a Sponsor-approved courier company where allowed by local regulations and agreed upon by the patients.

Use of local clinic or laboratory locations may be allowed for safety follow up in case the central lab cannot be used.

If onsite visit and home visit are not possible, the Investigator or delegate will perform a phone-call visit at each onsite planned visit to collect safety data and concomitant treatment. All data collected remotely will be properly documented in the patient's medical record and the study CRF.

[figure not shown]
If onsite visits are possible and there is a need to reduce the time spent on site to a minimum, the focus should be on IMP administration, collection of safety information (vital signs, adverse events) and safety blood collection (mainly biochemistry, hematology and ADA, if planned for the visit).

[figure not shown]
Contingencies implemented due to emergency will be documented.

[figure not shown]
For a regional or national emergency declared by a governmental agency, contingency procedures may be implemented for the duration of the emergency. The participants or their legally authorized representative should be verbally informed prior to initiating any changes that are to be implemented for the duration of the emergency (eg. study visit delays/treatment extension, use of local labs).

[figure not shown]
10.10 APPENDIX 10: ADDITIONAL APPENDICES

[figure not shown]
SF-12v2™ Health Survey © 1994, 2002 by QualityMetric Incorporated and Medical Outcomes Trust. All Rights Reserved.
SF-12® a registered trademark of Medical Outcomes Trust.
(SF12v2 Standard, US Version 2.0)

[figure not shown]

[figure not shown]

[figure not shown]

10.11 APPENDIX 11: ABBREVIATIONS

ADA:	anti-drug antibody
ADAMTS13:	a disintegrin and metalloproteinase with a thrombospondin type 1 motif13
ADE:	adverse device effect
ADL:	Activities of Daily Living
AE:	adverse event
AESI:	adverse event of special interest
aTTP:	acquired thrombotic thrombocytopenic purpura
CI:	confidence interval

COVID-19:	coronavirus disease 2019
cTnI:	cardiac troponin I
DMC:	Data Monitoring Committee
ECG:	electrocardiogram
eCRF:	electronic case report form
EQ-5D-5L:	5-level EuroQol 5-dimensional questionnaire
GCS:	Glasgow Coma Scale
HCRU:	healthcare resource utilization
HUS:	hemolytic uremic syndrome
ICF:	Informed consent form
ICU:	intensive care unit
IEC:	Independent Ethics Committee
IMP:	investigational medicinal product
IRB:	Institutional Review Boards
IST:	immunosuppressive therapy
ITT:	intent-to-treat
iTTP:	immune mediated thrombotic thrombocytopenic purpura
IV:	intravenous
LDH:	lactate dehydrogenase
LMWH:	low molecular weight heparin
mITT:	modified intent-to-treat
NIMP:	noninvestigational medicinal product
PD:	pharmacodynamics
PK:	pharmacokinetics
PQAT:	Patient's Qualitative Assessment of Treatment
SADE:	serious adverse device effect
SAE:	serious adverse event
SAP:	statistical analysis plan
SC:	subcutaneous
SD:	standard deviation
SF-12:	short form 12-item survey
SUSAR:	suspected unexpected serious adverse reaction
TE:	treatment-emergent
TMA:	thrombotic microangiopathy

TPE:	therapeutic plasma exchange
TTP:	thrombotic thrombocytopenic purpura
ULN:	upper limit of normal
ULvWF:	ultra-large von Willebrand factor
USADE:	unanticipated serious adverse device effect
vWF:	von Willebrand factor
WOCBP:	woman of childbearing potential

10.12 APPENDIX 12: PROTOCOL AMENDMENT HISTORY

The Protocol Amendment Summary of Changes Table for the current amendment is located directly before the table of contents (TOC).

10.12.1 Amended protocol 01 (02 May 2023)

This amended protocol (amendment 01) is considered to be substantial based on the criteria set forth in Article 10(a) of Directive 2001/20/EC of the European Parliament and the Council of the European Union.

OVERALL RATIONALE FOR THE AMENDMENT

The rationale for this protocol amendment is to allow sites to select which troponin and COVID-19 tests to use during Screening, and permit participants who have already received a dose of marketed caplacizumab prior to ICF signing to enroll in the study.

Protocol amendment summary of changes table

Section # and Name	Description of Change	Brief Rationale
1.2 Schema	Schema updated	Update
1.3 Schedule of Activities (SoA)	Footnotes added or modified for COVID-19 tests, HBV, HCV and HIV serology tests, serum creatinine, 12-lead ECG, platelet count, blood smear, and troponin test. Screening header corrected: "Screening (Day -2 to Day 1)" and footnote added to explain that baseline may occur on the same day as screening. Footnote added or modified to not perform some assessments locally at D1 if done at Screening, within 3 to 4 hours of Day 1 but all must still be performed centrally. Footnote and specifics added for IMP administration to participants who received and tolerated a single dose of marketed caplacizumab IV for the presenting episode of iTTP within 4 hours prior to enrollment.	Decrease participant's burden and permit some screening tests performed within a period of time prior to ICF signing to be used for Screening Correction of error Decrease participant's burden In many sites the standard of care is to administer the first dose of caplacizumab intravenously when iTTP is diagnosed clinically. This may occur before study enrollment. This SoC should not be withheld. These participants should still be permitted to enroll as long as the first dose for the presenting episode was given within 4 hours of ICF signing and is clearly documented in the eCRF.

Section # and Name	Description of Change	Brief Rationale
1.3 Schedule of Activities (SoA)	
Footnote modified for [REDACTED] [REDACTED]: they should be completed within 3 days of the baseline visit.
 
Footnote added for IMP diary: completion should begin after discharge, and paper diary can be used if eDiary is not available.
 
IMP/TPE administration deleted at 60H.
 
"(+/- 3 days after last dose intake)" added to early treatment discontinuation visit column header.
 
"+/-2H" to "24H, 30H, 36H" and "+/-3H" to "48H, 60H" added to column headers.
	
Update
 
Clarification
 
Correction of error
 
Clarification
 
Clarification

2. Introduction	Updated "European Commission" to "European Medicines Agency (EMA)"	Update
5.2 Exclusion criteria and throughout the document	
Text updated to allow the use of cTnT, high sensitivity cTnT, or high sensitivity cTnI tests.
 
Defining severe cardiac disease as "per Investigator discretion" or troponin level ">5x ULN".
	
Update
 
Troponin elevation is common in iTTP and minor elevations are not necessarily indicative of severe cardiac disease. The exclusion criterion has been modified to permit physician discretion and include a sample population more representative of the entire iTTP population.

6.4 Study intervention compliance	Updated	Update
8.1.5 Patient Reported Outcomes; 1.3 Schedule of activity (SoA)	Updated to reflect that caregiver is not allowed to complete the assessments alone.	Update
8.3.1 Time period and frequency for collecting AE and SAE information	Added collection of AEs from first caplacizumab administration to ICF signing.	Update
8.4 Pharmacokinetics	Added statement to use the left over samples for further research as described in Section 8.9	Update
8.7 Immunogenicity assessments	Added option of a functional neutralizing antibody assessment	Update
8.9 Use of biological samples and data for future research	Updated	Update
9.4 Sample size determination	Footnote added to Table 7	Update
10.1.4 Data protection	Wording updated	Update
10.1.6 Dissemination of clinical data and results	
Replacement of "ClinicalTrialsRegister.eu" by "euclinicaltrials.eu".
 
New standard texts added for results publication.
 
Clarification of the wording.
	Updated as per current template

Section # and Name	Description of Change	Brief Rationale
10.9 Appendix 9: Contingency measures for a regional or national emergency that is declared by a governmental agency	Updated	Contingency measures for COVID-19
10.12 Appendix 12: protocol amendment history	Section added	Update
Throughout the document	
Added the following text for TPE initiation: “including during the first 24 hours”.
 
Added the following text for caplacizumab discontinuation rules: “or 12 weeks, whichever occurs first”.
 
Addition of SARS-CoV-2 antigen test for screening
 
Reformatting of existing content when necessary.
 
Minor, editorial, stylistic changes as necessary.
 
Updated table of contents, section numbers, references, abbreviations as necessary.
	
Clarification
 
Consistency throughout document
 
Contingency measures for COVID-19
 
Update in accordance with Sponsor’s standards

3.6.3 Additional safety assessments.....	18
3.6.3.1 Laboratory variables, vital signs, and electrocardiograms.....	18
3.7 OTHER ANALYSES.....	20
3.7.1 Other variables and/or parameters	20
3.7.1.1 PK analyses	20
3.7.1.2 Quality of life analyses	20

3.7.1.3	Biomarker analyses.....	21
3.7.1.4	Immunogenicity	21
3.7.2	Subgroup analyses	27
3.8	INTERIM ANALYSES	28
4	SAMPLE SIZE DETERMINATION	29
5	SUPPORTING DOCUMENTATION	30
5.1	APPENDIX 1 LIST OF ABBREVIATIONS	30
5.2	APPENDIX 2 PARTICIPANT DISPOSITIONS	31
5.3	APPENDIX 3 DEMOGRAPHICS AND BASELINE CHARACTERISTICS, PRIOR OR CONCOMITANT MEDICATIONS	32
5.4	APPENDIX 4 DATA HANDLING CONVENTIONS	33
6	REFERENCES.....	39

LIST OF TABLES

Table 1 - Objectives and endpoints.....	6
Table 2 - Summary of primary estimand for main endpoints	8
Table 3 - Populations for analyses	9
Table 4 - Sorting of AE tables	16
Table 5 - Analyses of adverse events	17
Table 6 - Lower bound of 95% confidence interval given various assumed rates of participants achieving Remission without requiring TPE during the overall study period	29
Table 7 - Analyses window definition	34

VERSION HISTORY

This statistical analysis plan (SAP) for Study EFC16521 (MAYARI) is based on the amended protocol 01 dated 02 May 2023. There are no major changes to the statistical analysis features in this SAP.

The first participant was enrolled on 21 November 2022. This SAP is approved before the first interim analysis (IA) is conducted.

Major changes in the statistical analysis plan

SAP Version	Approval Date	Changes	Rationale
1	07-Jun-2024	Included in the SAP, and not in the protocol are: definitions of the enrolled population, the FAS population, sensitivity analyses for efficacy endpoints and subgroup analyses for the primary endpoint	Original version

1 INTRODUCTION

1.1 STUDY DESIGN

This is an open-label, single-arm, Phase 3, multicenter study to evaluate the efficacy and safety of caplacizumab and immunosuppressive therapy (IST) without first-line therapeutic plasma exchange (TPE) in adults with immune-mediated thrombotic thrombocytopenic purpura (iTTP).

The anticipated study duration per participant, without a recurrence while on therapy, is a maximum of approximately 24 weeks (ie, approximately 1 day for screening + maximum 12 weeks of treatment for the presenting episode + 12 weeks of follow-up). All participants will receive open-label caplacizumab daily until sustained disintegrin and metalloproteinase with a thrombospondin type 1 motif13 (ADAMTS13) activity normalization ($\geq 50\%$) is achieved at 2 consecutive visits, after platelet count normalization (defined as $\geq 150 \times 10^9/L$ for 2 consecutive values) or 12 weeks of caplacizumab treatment, whichever occurs first.

For participants who experienced a first clinical recurrence (exacerbation or relapse) during the overall study period, the ongoing treatment plan may be adjusted including a start or re-start of TPE and adjustment of IST regimen and caplacizumab therapy. In case that caplacizumab treatment is maintained for a first clinical recurrence, the visit schedule will be the same as during the initial treatment period.

[figure not shown]
The primary analysis will be conducted after study completion of all participants, ie, when all the participants will have discontinued from the study.

In addition, an interim analysis (IA) will be conducted after the first 30 participants with baseline ADAMTS13 activity of $<10\%$ have completed the study (eg ended treatment period per protocol and completed the follow-up period of 12 weeks) (see [Section 3.8](#) for further details). A Data Monitoring Committee (DMC), independent from the Sponsor, will be appointed to monitor the safety and the scientific integrity of this study on an on-going basis, and to provide in a timely fashion appropriate recommendations to the Sponsor.

1.2 OBJECTIVES AND ENDPOINTS

Table 1 - Objectives and endpoints

	Objectives	Endpoints
Primary	
To evaluate the efficacy of caplacizumab in combination with immunosuppressive therapy (IST) without therapeutic plasma exchange (TPE) in adults with immune mediated thrombotic thrombocytopenic purpura (iTTP).	
Proportion of participants achieving Remission without requiring TPE during the overall study period Remission is defined as sustained Clinical Response (sustained platelet count $\geq 150 \times 10^9/L$ and lactate dehydrogenase [LDH] $<1.5 \times$ upper limit of normal [ULN] and no clinical evidence of new or progressive ischemic organ injury for at least 2 consecutive visits) with either (a) no TPE and no anti- von Willebrand factor (anti-vWF) therapy for ≥ 30 days (Clinical Remission), or (b) with attainment of a disintegrin and metalloproteinase with a thrombospondin type 1 motif13 (ADAMTS13) $\geq 50\%$ (Complete ADAMTS13 remission), whichever occurs first.

	Objectives	Endpoints
Secondary	
 • To evaluate the need for therapeutic plasma exchange in adult participants with an episode of iTPP treated with caplacizumab and IST. • To evaluate the safety of caplacizumab in combination with IST without first-line TPE in adults with iTPP. • To evaluate the effect of treatment with caplacizumab and IST without first-line TPE on clinical response. • To evaluate the effect of treatment with caplacizumab and IST without first-line TPE on restoring platelet counts. • To evaluate the effect of treatment with caplacizumab and IST without first-line TPE on refractory disease. • To evaluate the effect of treatment with caplacizumab and IST without first-line TPE on clinically relevant iTPP-related events consisting of iTPP-related mortality. • To evaluate the effect of treatment with caplacizumab and IST without first-line TPE on clinically relevant iTPP-related events consisting of exacerbation of iTPP. • To evaluate the effect of treatment with caplacizumab and IST without first-line TPE on clinically relevant iTPP-related events consisting of relapse of iTPP. 	
 • Proportion of participants achieving Remission during the overall study period. • Proportion of participants who require TPE during the on-treatment period. • The occurrence of adverse events (AEs), serious adverse events (SAEs), and adverse events of special interest (AESIs) during the treatment-emergent (TE) period. • Proportion of participants achieving Clinical Response during on-treatment period and during the overall study period. Clinical Response is defined as sustained platelet count $\geq 150 \times 10^9/L$ and LDH $<1.5 \times ULN$ and no clinical evidence of new or progressive ischemic organ injury for at least 2 consecutive visits. • Time to platelet count response defined as time from start of treatment to initial platelet count $\geq 150 \times 10^9/L$ that is sustained for ≥ 2 days. • Proportion of participants refractory to therapy defined as lack of sustained platelet count increment (over 2 consecutive days) or platelet counts $<50 \times 10^9/L$ and persistently elevated LDH ($>1.5 \times ULN$) despite 5 days of treatment during the on-treatment period. • Proportion of participants with thrombotic thrombocytopenic purpura (TTP)-related death during the on-treatment period and during the overall study period • Proportion of participants with a clinical exacerbation of iTPP during the on-treatment period and during the overall study period. Clinical Exacerbation is defined as after a Clinical Response and before a Clinical Remission, platelet count decreases to $<150 \times 10^9/L$ (with other causes of thrombocytopenia excluded), with or without clinical evidence of new or progressive ischemic organ injury, within 30 days of stopping TPE or anti-vWF therapy. • Proportion of participants with a clinical relapse of iTPP during the on-treatment period and during the overall study period. Clinical Relapse is defined as after a Clinical Remission, platelet count decreases to $<150 \times 10^9/L$ (with other causes of thrombocytopenia ruled out), with or without clinical evidence of new ischemic organ injury. A Clinical Relapse must be confirmed by documentation of severe ADAMTS13 deficiency ($<10\%$).
Other		

Objectives	Endpoints

1.2.1 Estimands

Primary estimand defined for the primary endpoint is summarized in [Table 2](#). More details are provided in [Section 3.2](#).

Table 2 - Summary of primary estimand for main endpoints

Endpoint Category (estimand)	Estimands			
	Endpoint	Population	Intercurrent event(s) handling strategy	Population-level summary (Analysis and missing data handling)
Primary objective: To evaluate the efficacy of caplacizumab in combination with immunosuppressive therapy (IST) without therapeutic plasma exchange (TPE) in adults with immune mediated thrombotic thrombocytopenic purpura (iTTP)				
Primary endpoint (treatment policy estimand)	Remission	All enrolled participants who received at least 1 dose of IMP and with an ADAMTS13 activity <10% at baseline	Regardless of adherence to study intervention and/or study discontinuation	Proportion of participants achieving Remission without requiring TPE during the overall study period

2 ANALYSIS POPULATIONS

The following populations for analyses are defined.

Table 3 - Populations for analyses

Population	Description
Screened	All participants who sign the informed consent form (ICF).
Enrolled	All participants from the screened population who met the eligibility criteria (ie, who are not screen failures). Participants who received caplacizumab and did not meet inclusion or met exclusion criteria are not enrolled, such as a participant with a confirmed alternate diagnosis.
Full Analysis Set (FAS)	All enrolled participants, who received at least 1 dose of the investigational medicinal product (IMP, ie, Caplacizumab). The FAS population will be used only for sensitivity analyses.
Modified ITT (mITT)	All enrolled participants who received at least 1 dose of IMP and with an evaluable primary endpoint. The mITT population will be the main efficacy analysis population. The primary endpoint is evaluable when the participant has an ADAMTS13 activity of <10% at baseline.
Safety	All enrolled participants who received at least 1 dose of IMP.
Pharmacokinetic (PK)	All enrolled and treated participants (safety population) with at least one post-baseline PK sample with adequate documentation of dosing and sampling dates and times.

Enrolled participants for whom it is unclear whether they took the IMP will be considered as exposed and will be included in the safety population.

To note that amended protocol 01 permits participants who have already received a dose of marketed caplacizumab for the presenting episode of iTTP within 4 hours prior to enrollment/ICF signing to enroll in the study. Consequently, participants exposed to a single dose of marketed caplacizumab within 4 hours prior to enrollment will be included in any analysis population.

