3 STATISTICAL ANALYSES

3.1 GENERAL CONSIDERATIONS

In general, continuous data will be summarized using the number of observations available, mean, standard deviation (SD), median, interquartile range (Q1, Q3), minimum, and maximum.

Categorical and ordinal data will be summarized using the count and percentage of participants.

No pre-specified success criterion or formal statistical hypothesis testing is planned. No statistical adjustment on interim analyses is planned.

When the notion of IMP is mentioned in the SAP, this refers to the study IMP.

The baseline value is defined as the last available value before the first dose of IMP, including participants who have received a dose of marketed caplacizumab for the presenting episode of iTP within 4 hours prior to enrollment. For participants enrolled but not treated with IMP, the baseline value is defined as the last available value before enrollment.

Efficacy endpoints derived from laboratory data (platelet count, lactate dehydrogenase [LDH], cardiac troponin I [cTnI], creatinine, ADAMTS13 activity) will be analyzed using central measurements, unless they are missing for a visit but the local value available, in which case the local value will be used under certain conditions (see [Section 5.4](#)). A central measurement will be considered missing if the recorded status is “NOT DONE” and there is a reason for this status or if status is “NOT PERFORMED”.

The observation period will be divided into 4 segments:

- The **pre-treatment period** is defined as the period up to the first caplacizumab administration (whatever marketed or study IMP).
- The **treatment-emergent (TE) period** is defined as the period from the first caplacizumab administration (whatever marketed or study IMP) up to the last caplacizumab administration **+ 28 days**. The TE period includes the following 2 periods:
 - The **on-treatment period** is defined as the period from the caplacizumab administration (whatever marketed or study IMP) to the last administration of caplacizumab.
 - The **residual treatment period** is defined as the period from the end of the on-treatment period to the end of the TE period.
- The **post TE period** is defined as the period from the end of the TE period.

The **overall study period** is defined as the time from the first caplacizumab administration (whatever marketed or study IMP) until the end of the study.

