3.6 SAFETY ANALYSES

All safety analyses will be performed on the safety population as defined in [Section 2](#), unless otherwise specified.

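### As written, SAP Table 3 drops a participant given study drug and later judged ineligible from Enrolled, and so from Safety, FAS, mITT and PK, unlike the protocol's Safety population

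*SAP*

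**What the plan says.** SAP Section 2, Table 3 defines Enrolled as "All participants from the screened population who met the eligibility criteria (ie, who are not screen failures") and then adds: "Participants who received caplacizumab and did not meet inclusion or met exclusion criteria are not enrolled, such as a participant with a confirmed alternate diagnosis".

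The Safety row reads "All enrolled participants who received at least 1 dose of IMP". The FAS and mITT rows also start from enrolled participants, and PK is a subset of Safety. Two notes follow the table. One covers uncertain intake: "Enrolled participants for whom it is unclear whether they took the IMP will be considered as exposed and will be included in the safety population". The other covers pre-study dosing: "participants exposed to a single dose of marketed caplacizumab within 4 hours prior to enrollment will be included in any analysis population".

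On terms, SAP Section 3.1 states: "When the notion of IMP is mentioned in the SAP, this refers to the study IMP". The same section uses the word caplacizumab for either source; the pre-treatment period, for example, "is defined as the period up to the first caplacizumab administration (whatever marketed or study IMP").

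SAP Section 3.6 sets the default: "All safety analyses will be performed on the safety population as defined in" Section 2, unless something else is specified.

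The Safety row in protocol Section 9.1, Table 6 is almost identical to the SAP's. The protocol has no formal definition of enrolled and no FAS; its nearest set is ITT. The SAP version history discloses that the Enrolled and FAS definitions are new in the SAP.

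**The concern.** Safety tables should count everyone given study drug. Here membership can depend on a judgement made after dosing, in an open-label trial that starts treatment on a clinical diagnosis before the ADAMTS13 result is known. A participant who received several doses, had an adverse event, and was then given another diagnosis could be absent from the exposure, AE, laboratory and death summaries. FAS, the only sensitivity set for efficacy, would lose the same person.

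The loss is confined to the summary tables. Adverse event collection and 24-hour reporting (protocol Section 8.3.1) and DMC and sponsor review (protocol Section 10.1.5.1) do not depend on this definition.

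**Working it through.** **The plan's own figure.** The sample-size figure is not in dispute. The 95% Wilson interval is [p + z²/2n ± z√(p(1−p)/n + z²/4n²)] / (1 + z²/n) with z = 1.96. For 39/55 (70% of 55, rounded up) the lower bound is 57.9%, matching the stated 58%.

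**Set membership.** Take a participant given study IMP and later judged ineligible.

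| Set | SAP Table 3 | Protocol Table 6 |
|---|---|---|
| Enrolled / ITT | No | Yes |
| Safety | No | Yes |
| FAS | No | Not defined |
| mITT | No | Only if baseline ADAMTS13 <10% |
| PK | No | Yes, if there is a documented post-baseline sample |

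The protocol column rests on three provisions. Only enrolled participants may be given study intervention (Section 6.2). Treatment starts while the ADAMTS13 result is pending (Section 4.1). Those who stop permanently stay in the study for follow-up (Section 7.1.1). The two Safety rows therefore read alike but select different people, because enrolled means different things.

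**Does anything restore the person?** The uncertain-intake note applies only to those already enrolled. The marketed-dose note concerns people who go on to enroll. SAP Section 3.6.2 adds deaths among enrolled-but-untreated participants, not treated-but-not-enrolled ones. SAP Section 5.2 counts screen failures with reasons and summarizes deviations on Enrolled. Protocol Section 5.4 requires any SAE of a screen failure to be recorded, but the SAP plans no AE table for them.

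**Who is at risk?**
- Baseline ADAMTS13 of 10% or more does not by itself appear to remove someone. SAP Section 5.3 tabulates the <10/≥10% classes on FAS, and protocol Section 9.4 enrolls about 61 to obtain 55 below 10%. The gap of 6 is therefore not used as a bound.
- Exclusions E 03 and E 04 concern causes known at entry, so a cause found later does not on its face breach them.
- What remains is eligibility errors found after dosing, and the SAP's own example of a confirmed alternate diagnosis. That example can arise after dosing: I 02 asks for ADAMTS13 confirmation within 48 hours, the central result takes 3 to 4 days (Section 4.1), and a central result above 20% prompts consideration of other diagnoses (Section 7.1.1).

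**Exposure by then.** The schedule in protocol Section 1.3.4 gives study drug at 0 h, 4–6 h, 24 h and 48 h, then daily. That is 3 doses before 48 h, 4 before 72 h and 5 before 96 h, or one fewer if a marketed IV dose replaced the first.

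**Size, with the number removed (k) assumed.**
- Share missing from Safety if k come out of 61, for k = 0, 1, 2, 3: k/61 = 0%, 1.6%, 3.3%, 4.9%.
- If k come on top of 61: k/(61 + k) = 0%, 1.6%, 3.2%, 4.7%.
- One person removed, who had the only event of its kind: reported 0/60, with upper limit z²/(n + z²) = 3.84/63.84 = 6.0%. The full count is 1/61 = 1.6%, Wilson 0.3% to 8.7%.
- mITT changes only if someone below 10% also fails another criterion. Taking 38/55 = 69.1% as an example near 70%, removing a non-responder gives 38/54 = 70.4% (+1.3 points) and removing a responder gives 37/54 = 68.5% (−0.6 points).

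**The case against.** The best defence is that the sentence is about marketed drug only. E 13 excludes people given caplacizumab for the presenting episode more than 4 hours before enrollment; they received the drug and met an exclusion criterion. The SAP follows amendment 01, which opened enrollment to people already given a marketed dose, and a note on that sits directly below the table. The Enrolled row explains eligibility by not being a screen failure, which in both documents is a status fixed before dosing. The SAP also lists no treated-but-not-enrolled category anywhere. And if Enrolled meant verified eligibility, the deviation summary on Enrolled could never contain an eligibility deviation.

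This makes the narrow intent plausible, and it stands as a statement of what the authors may have meant. It does not settle what the text does. The sentence is not limited to marketed drug, whereas the SAP writes the word marketed when it means only that. The FAS row equates IMP with caplacizumab. On the narrow reading the sentence adds nothing to FAS, mITT or Safety, which already require study IMP. A confirmed alternate diagnosis could surface before dosing, but it also fits the protocol's post-dosing route.

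It is also fair that the conflict with the protocol is inferred from several sections rather than from a formal definition, that protocol Section 7.1.1 handles a central result above 20% as discontinuation with follow-up, and that the count may be zero.

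**Conclusion.** The concern holds as written. A literal application of Table 3 excludes a dosed, later-ineligible participant from Enrolled, FAS, mITT, Safety and PK, and for Safety this departs from what the protocol's own rules imply. The authors may have intended something narrower, but a programmer following the text would not know that.

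The effect is small in expectation and unquantified in fact: k is not given in the documents and may be 0. Its importance is that in a single-arm study of about 61, one removed participant can turn a reported event into none. Any effect on the primary estimate is about a point and descriptive, since no test or success criterion is planned. This should be fixed, but it does not threaten the trial's main result.

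**What to change.** 1. Define Safety and FAS as all participants who received at least one dose of study IMP, regardless of ineligibility or an alternate diagnosis identified later. Keep the rule that uncertain intake counts as exposed.
2. Define Enrolled by the documented decision to enroll before dosing, not by having met the criteria. Deleting the carve-out sentence alone is not enough, because the first sentence of the row would still require eligibility.
3. Limit the carve-out sentence to people never given study IMP.
4. Report ineligible-but-dosed participants as protocol deviations, not screen failures.
5. Keep baseline ADAMTS13 <10% as the mITT criterion.

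The cost is SAP wording only, with no new data. Safety and FAS counts and rates may move slightly in either direction. If the narrow meaning was intended all along, no result changes and the ambiguity is gone.
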